4.5 Examinations

The following clinical tests will be performed during the project cf. figure 2.

	Enrollment	Inclusion (Baseline)	After 3 months	After 6 months	After 9 months	After 12 months
Informed consent	X					
Eligibility screening	X					
Blood sample		X	X	X	X	X
Tracheal aspirate and nasal swab		X				X
Lung function measurement (Spirometry)		X				X
Weight		X				X
Height		X				
COPD Assessment Test (CAT)		X				X
MRC-dyspnoea scale		X	X	X	X	X

Figure 2: An overview of examinations that each participant will undergo. The blood test can be performed either at the participant's home or at the outpatient clinic, with intervals of 3, 6, and 9 months.

Blood tests: Electrolyte parameters (sodium, potassium, albumin, creatinine, hemoglobin), liver parameters (conjugated bilirubin, ALT, alkaline phosphatase, INR, LDH), infection parameters (CRP, white blood cell differential count, thrombocytes), D-dimer and HbA1c.

Patients with COPD enrolled in the COPERNICOS clinical trial exhibit physical frailty due to the severity of their illness. Therefore, attendance at one of the trial sites in general is both demanding and stressful for the participants. To reduce the stress and to ease the access for the COPD patients to participate in the trial, the blood tests after 3, 6 9 and 12 months can be performed in the participants' home. Otherwise, they will be performed at one of the local trial sites. It's important to highlight that the full 12-month follow-up, including spirometry, will be conducted in patients' homes if they are unable to visit the trial sites. If the blood test is performed at the participants' home, it will be performed by trial staff either a doctor, a nurse, or a medical student. All staff will be trained in accordance with the current ICH-GCP guidelines. However, the investigator has the ultimate responsibility for all trial related medical decisions. The blood tests will be analyzed by the already approved laboratories for the trial. We aim to ensure that participants, needing the blood test to be taken at home more than one time, will be visited by the same trial staff to contribute to continuity for the patients. The blood tests will only be performed by doctors, nurses or medical student, who will follow all applicable and relevant guidelines and our standard operating procedures (SOP) on handling and storage of blood tests set by the Capital Region of Denmark ("Region Hovedstaden").

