4.6 Data Collection

Data processing, statistical analysis and publication of the data material will be performed by a PhD student (coordinating investigator) together with health professionals (primary and secondary investigators) from the participating pulmonary medical outpatient clinics. The randomized trial started with the inclusion of participants 05JUL2021, and the last participant is expected to be

included by 31AUG2025. Data collection ceases 31AUG2026, and the project is scheduled to run until 31AUG2026.

A nurse will be responsible for collecting baseline data, performing lung function measurement, weight and height at baseline and the 12-month follow-up as well as performing blood sampling and questionnaires at three-, six- and nine-month follow-ups, according to Fig. 2. Data will be obtained via the electronic health record. Medical decisions are made by doctors only. Proper handling, storage, and delivery of medication and the primary daily project management is handled by the coordinating investigator. Recruitment, medical examinations, and distribution and accounting of medication will be assisted by primary investigators at each centre.

The data collected will be treated confidentially and only by personnel associated with the project. This includes demographic data, health status, current illnesses, medications, medicinal side effects, hospital admissions, and results from various examinations during the trial. Data will be reported in Electronic Case Report Forms (eCRF) specific for each participant. The data is encrypted, stored in online servers and protected by the Data Protection Authority through various security precautions. The physical copies of the CRF are kept in locked archives on the involved departments for 5 years.

Data in eCRF will be handled by the investigator at each centre and in accordance with the Law for Data Protection and the Danish Law for Privacy Regulation.

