5.2 Secondary Endpoints

ICS and Azithromycin

- “Days alive and out of hospital within 365 days after recruitment” (continuous data: analysis with T-test)Death or “uncontrolled AECOPD tendency”⁷ within 365 days.
- Number of moderate/severe exacerbation within 365 days
- Cumulative dose of inhaled corticosteroids within 365 days
- Cumulative dose of systemic corticosteroids within 365 days
- Change in lung function (Δ FEV1) from baseline to 365 days

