5.3 Exploratory

ICS

- Change in blood eosinophils from baseline to 365 days (eosinophilic trajectories)

⁷ ≥ 3 exacerbations within 12 months

- New diagnosis of diabetes mellitus within 365 days
- Change in HbA1c from baseline to 365 days
- Antibiotic-requiring infections within 365 days

ICS and Azithromycin

- Difference in respiratory microbiota abundance and diversity from baseline to 12 months between treatment arms
- Difference in immunological profile including cytokines and chemokines in the upper airways from baseline to 12 months between treatment arms
- Change in COPD-related quality of life (Based on COPD Assessment Test - CAT) from baseline to 365 days
- Number who progress to MRC -dyspnea score from < 3 to ≥ 3 anytime during follow-up (assessed every 3 months).
- Number of admission requiring non-invasive ventilation (NIV) treatment or admissions to intensive care within 365 days
- Mortality within 365 days

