5.3 Data analysis

The four treatment groups will be compared in terms of endpoints at inclusion and follow-up visits every 3 months from trial inclusion with standard statistical tests such as t-test (Dichotomous outcomes), chi-squared test, Fisher's exact test, and time-to-event analyses.

Recurrence of AECOPD, the period between index AECOPD and the next AECOPD, and number of admission-requiring NIV treatment within 365 days are analyzed using Fisher's exact test or Chi-

squared test. Time to AECOPD within 365 days and number of hospitalization-requiring exacerbations within 365 days will be analyzed with t-test and Cox proportional-hazards regression model (unadjusted and adjusted). Mortality rate within 365 days will be analyzed with Chi-squared test or Fisher's exact test (unadjusted) and with Cox proportional-hazards regression model (adjusted).

New onset of diabetes during the study period or occurrence of antibiotic-requiring infections within 365 days will be analyzed using Fisher's exact test or Chi-squared test. Changes in lung function, health-related quality-of-life (CAT), and level of dyspnea (MRC) will be analyzed using analysis of variance (ANOVA). The cumulative ICS dose will be analyzed as mean total cumulative dose from recruitment to end of the study period using t-test, Wilcoxon signed-rank test or Mann-Whitney U test.

6. Risks and Side Effects

Possible side effects from the use of ICS (Beclometasondipropionat) according to pro.medicin.dk are:

Common (1-10%): Pharyngitis, Coughing, Hoarseness, Headache, Candidiasis.

Uncommon (0.1-1%): Blurry vision, Dizziness, Tremor.

Rare (0.01-0.1%): Allergic reactions, Angioedema, Bronchospasm.

Very rare (<0.01%): Adrenal insufficiency. Eosinophilic pneumonia. Erythema, purpura. Decrease in bone mineral density. Glaucoma, cataract. Growth retardation.

Unknown prevalence: Disturbed behavior, Aggressiveness, Anxiety, Depression, Hallucinations, Hyperactivity, Hypercorticism.

Possible side effects from the use of Azithromycin according to pro.medicin.dk are:

Very common (>10%): Abdominal pain, diarrhea, flatulence, nausea.

Common (1-10%): Tiredness or weakness. Decreased appetite. Vomiting, taste perversion. Decreased lymphocyte count. Decreased serum bicarbonate. Arthralgia. Headaches, Paresthesia, Dizziness. Skin itching, rash. Visual disturbances.

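### FEV1 and CAT change are analysed by ANOVA with no baseline covariate, which costs some precision, and the ANOVA named for MRC does not estimate the MRC endpoint as defined

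*Protocol*

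**What the plan says.** Section 5.3 Data analysis assigns one method to three measures: "Changes in lung function, health-related quality-of-life (CAT), and level of dyspnea (MRC) will be analyzed using analysis of variance (ANOVA)." The sentence names no covariate. Elsewhere the protocol mentions adjustment in two places: for the other randomised intervention in the main analysis (Section 5), and for Cox models that it labels as adjusted (Section 5.3 Data analysis).

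The endpoints themselves are defined as follows:

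- **FEV1**, secondary (Section 5.2): change "from baseline to 365 days".
- **CAT**, exploratory (Section 5.3 Exploratory): "Change in COPD-related quality of life (Based on COPD Assessment Test - CAT) from baseline to 365 days".
- **MRC**, exploratory (same section): "Number who progress to MRC -dyspnea score from < 3 to ≥ 3 anytime during follow-up (assessed every 3 months)."

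The baseline values are collected by design. The schedule in Section 4.5 is described as "An overview of examinations that each participant will undergo". It marks spirometry and CAT at baseline and 12 months, and MRC at baseline and at 3, 6, 9 and 12 months. Section 4.6 agrees for spirometry, making a nurse responsible for "performing lung function measurement, weight and height at baseline and the 12-month follow-up".

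**The concern.** There are two separate issues in the one sentence.

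First, a change score subtracts the whole baseline value, which amounts to fixing the regression slope on baseline at 1. ANCOVA estimates that slope. When the two measurements are imperfectly correlated, a slope of 1 is too steep and the treatment difference carries avoidable noise. Confidence intervals for FEV1 and CAT would be wider than the same data allow.

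Second, the MRC endpoint is a yes/no outcome, and only participants who start below 3 can meet it. An ANOVA of change in MRC level answers a different question. If the Data analysis section is followed, the reported MRC result will not be a result for the listed endpoint. If the endpoint definition is followed, the named method has to be abandoned.

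**Working it through.** **Part 1: FEV1 and CAT**

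The protocol gives no standard deviation, correlation, effect size or power for either measure, so there is no figure of its own to reproduce.

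Inputs:

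- 444 participants, 222 on each side of each factorial comparison (Section 5).
- Two-sided 5%, corresponding to the one-sided 2.5% that Section 5 uses for the primary endpoint. It is borrowed here for illustration only.
- r, the baseline to 12-month correlation: **assumed**, 0.5 to 0.9.
- Equal variance s² at both times: **assumed**.

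Per-participant variance entering the treatment comparison:

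- Change score: 2s²(1 − r)
- ANCOVA: s²(1 − r²) = s²(1 − r)(1 + r)
- Ratio, ANCOVA to change score: (1 + r)/2

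| r | Change score (s² = 1) | ANCOVA (s² = 1) | Ratio | Extra participants for equal precision (1/ratio − 1) | 444 × ratio | Power of ANOVA on change where ANCOVA has 80% |
|---|---|---|---|---|---|---|
| 0.5 | 1.00 | 0.75 | 0.75 | 33% | 333 | 67.9% |
| 0.7 | 0.60 | 0.51 | 0.85 | 18% | 377 | 73.3% |
| 0.8 | 0.40 | 0.36 | 0.90 | 11% | 400 | 75.7% |
| 0.9 | 0.20 | 0.19 | 0.95 | 5% | 422 | 78.0% |

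The column 444 × ratio is the number of participants in whom ANCOVA would be as precise as ANOVA on change in all 444.

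A simulation of 3,000 trials of 444 participants at each of r = 0.5, 0.7 and 0.9 gave variance ratios of 0.76, 0.84 and 0.95. Both estimators centred on the true difference of zero. The simulation therefore confirms the precision loss and shows no bias.

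The direction does not depend on r: (1 + r)/2 is below 1 for every r below 1. Nor does it need equal variances. With standard deviations s₀ at baseline and s₁ at 12 months, the change-score variance minus the ANCOVA variance is s₀² + s₁² − 2r·s₀·s₁ − s₁²(1 − r²) = (s₀ − r·s₁)², which is never negative.

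**Part 2: MRC**

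No arithmetic is needed. The two sections side by side:

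| | Section 5.3 Exploratory | Section 5.3 Data analysis |
|---|---|---|
| Quantity | Number crossing from below 3 to 3 or more | Change in MRC level |
| Type | Binary per participant | Numeric, compared as means |
| Who can contribute an event or a change | Only those below 3 at baseline | Everyone |
| Timing | Any of the 3-monthly assessments | Not stated |

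Two illustrative participants show the difference. One goes from 2 to 3 at month 6 and is back at 2 at month 12: an event for the endpoint, but a change of zero at 12 months. Another goes from 3 to 4: a change of +1, but not an event. The mean change cannot be turned back into the count.

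**The case against.** **A change score already uses the baseline.** This is correct: it enters by subtraction. What is missing is the baseline as a covariate, and the point is confined to that.

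**The analysis is not wrong.** Also correct. A reader might infer that regression to the mean biases the comparison. The documents do not support that: under randomisation it acts equally on the groups on average, and the simulation found both estimators unbiased. Chance baseline imbalance is already counted in the variance ratio and is not a second harm.

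**Covariates are normally left to the SAP.** Often so, and the sentence does not forbid them. But it names ANOVA on changes, and the same section marks its Cox models as adjusted without marking this analysis so. Taken at its word, the protocol fixes the less precise method. This limits the point to an efficiency recommendation.

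**The size rests on an unseen correlation.** This stands. At r of 0.8 to 0.9 the loss is 5% to 10%. The 33% figure belongs to the low end of an assumed range and should not be quoted alone.

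**HbA1c and blood eosinophils.** A reader might extend the criticism to these changes, since both are also measured at baseline. The ANOVA sentence does not name them and the protocol assigns them no specific method, so there is no stated choice to correct.

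**The general list of tests could cover MRC.** The opening sentence of Section 5.3 Data analysis lists chi-squared and Fisher's exact tests for the endpoints, and the ANOVA could be read as an additional summary of MRC. This is the best defence, but it does not settle the matter. ANOVA is the only method attached to MRC by name, and nothing says it is additional. The general sentence also labels the t-test as the one for dichotomous outcomes, so it is a poor guide to how a binary count would be tested.

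**Conclusion.** Both parts hold, at minor severity.

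For FEV1 and CAT, ANOVA of change is valid but gives up precision that the planned baseline measurements would provide at no cost. The ANCOVA variance is lower by 25%, 15% or 5% at r = 0.5, 0.7 or 0.9. That the loss exists follows from algebra. Its size rests on the assumed r and on equal variances. It also takes baseline values to be available as scheduled; how many will in fact be missing is unknown.

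For MRC, the two parts of the protocol name different quantities, and the named analysis does not estimate the stated endpoint. This rests on the text alone.

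The trial is sized on the exacerbation/death endpoint in Section 5, which this does not touch. The endpoints affected are one secondary (FEV1) and two exploratory (CAT and MRC).

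**What to change.** In Section 5.3 Data analysis, replace the ANOVA sentence with two statements:

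1. Change in FEV1 and in CAT is analysed by ANCOVA. The outcome is the 12-month value or the change (the treatment estimate is the same either way once baseline is in the model). The model includes the randomised ICS strategy, the randomised azithromycin or placebo assignment, the baseline value of the same measure, and the stratification factors in Section 5 (site, age group, and hospital-requiring exacerbations in the past 12 months).
2. MRC progression is analysed as a binary outcome among participants with baseline MRC below 3, as the difference in the proportion reaching 3 or more at any 3-monthly assessment. If a mean change in MRC is also wanted, list it as a separate exploratory summary.

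The cost is a short wording change in the protocol, carried into the SAP before unblinding. All the variables are already scheduled for collection, so no new data are needed.

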2.2 Microbiota objectives

ICS

- Whether a strategy of eosinophil-guided administration of ICS in COPD patients with GOLD class E and/or $FEV_1 < 30\%$ leads to a change in (i) the respiratory microbiota abundance and diversity and (ii) the immunological profile in comparison to continuous triple therapy (ICS/LABA/LAMA).

Azithromycin

- Whether prophylactic low dose Azithromycin in COPD patients with GOLD class E and/or $FEV_1 < 30\%$ leads to changes in (i) the respiratory microbiota abundance and diversity and (ii) the immunological profile.

3. Hypotheses

ICS primary

- In COPD patients with GOLD class E and/or $FEV_1 < 30\%$, an eosinophil-guided administration of ICS treatment regimen is associated with no apparent loss of efficiency⁵.

ICS secondary

- In COPD patients with GOLD class E and/or $FEV_1 < 30\%$, eosinophil-guided administration of ICS will reduce the use of inhaled corticosteroids by $> 25\%$ ⁶.

⁵ Measured by "admissions with COPD exacerbation or death from all causes within 365 days

⁶ Measured by budesonide equivalent doses

- In COPD patients with GOLD class E and/or FEV₁ < 30%, eosinophil-guided administration of ICS will reduce the number of ICS related side effects.
- The respiratory microbiota have a composition of less "pathogenic" bacterial species in COPD patients with GOLD class E and/or FEV₁ < 30%, treated with the eosinophil-guided administration of ICS regimen compared to those treated with continuous triple therapy (ICS/LABA/LAMA) regimen.
- The complexity of the respiratory microbiota is lower among COPD patients with GOLD class E and/or FEV₁ < 30%, treated with continuous triple therapy (ICS/LABA/LAMA) regimen than among those treated with the eosinophil-guided administration of ICS regimen.
- The immunological profile of the upper airways changes in COPD patients with GOLD class E and/or FEV₁ < 30% treated with the eosinophil-guided ICS regimen compared to those treated with continuous triple therapy (ICS/LABA/LAMA) regimen.

Azithromycin primary

- In COPD patients with GOLD class E and/or FEV₁ < 30%, the use of low dose Azithromycin can result in a reduction in admissions with COPD exacerbation or death from all causes within 365 days" as compared to placebo.

Azithromycin secondary

- The difference in composition of the respiratory microbiota is substantial when COPD patients with GOLD class E and/or FEV₁ < 30% are treated with prophylactic low dose Azithromycin

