8.1 Remuneration

Participants will not receive remuneration for project participation, but the cost of Azithromycin/placebo treatment during the trial period will be covered by the sponsor.

9. Publications of Trial Results

The trial is a part of a PhD thesis. The results from the trial will be published regardless of whether they are positive, negative, or inconclusive. The trial will be registered and published at clinicaltrials.gov, clinicaltrialsregister.eu as well as published in an international peer-reviewed scientific journal and in The Journal of the Danish Medical Association. At least one publication in a high impact scientific journal is expected. If publication in a scientific journal is not possible, the results will be published as an online report. In addition, a summary of the results will be submitted

to the CTIS and the Clinical Trials database (www.clinicaltrials.gov) as soon as possible and no later than one year after the trial has ended.

10. Scientific Perspective

AECOPD are often accompanied by markedly reduced lung function and increased likelihood of progression of COPD and mortality. In many cases, the illness progression following an exacerbation is irreversible. Therefore, the everyday life of COPD patients is often characterized by fear and anxiety of these acute exacerbations. In addition to the risk of exacerbations, the risk of side effects from the medical treatment of COPD often creates additional concerns for COPD patients. Corticosteroids in the dosages given both for maintenance and for AECOPD carry high risks for the patient: dysregulation of glucose hemostasis (17), high risk of pneumonia and other infections (23, 24), and emergence or worsening of osteoporosis and the consequent fractures (8). Such side effects can lead to a vicious cycle of anxiety, physical deconditioning, muscle wasting, loss of social life, increased risk of further AECOPD, more corticosteroids, and again more side effects. We believe that this trial has the potential to impact the current COPD guidelines seeing that it can provide relevant information for the development of a treatment plan that has the potential to reduce the usage of ICS by 80%⁸, minimize ICS-induced complications and increase the patients' quality of life.

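### The secondary hypothesis of a more than 25% reduction in ICS use is not tied to any of the tests named for cumulative ICS dose, so a significant result would not establish it

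*Protocol*

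**What the plan says.** Three places in the protocol bear on this point.

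- **Section 3, ICS secondary hypotheses.** In the trial population, "eosinophil-guided administration of ICS will reduce the use of inhaled corticosteroids by" more than 25%. The footnote fixes the unit: "Measured by budesonide equivalent doses".
- **Section 5.2, Secondary Endpoints.** The endpoint is "Cumulative dose of inhaled corticosteroids within 365 days".
- **Section 5.3, Data analysis.** The summary measure and the first test are given together: "The cumulative ICS dose will be analyzed as mean total cumulative dose from recruitment to end of the study period using t-test". The full choice of tests is "using t-test, Wilcoxon signed-rank test or Mann-Whitney U test".

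The protocol nowhere turns the 25% into a null value, a ratio or percentage estimate, or a confidence limit.

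**The concern.** The hypothesis has a threshold and the named analysis does not. A t-test or Mann-Whitney test in its usual form is a test against no difference. With more than 200 participants per side, such a test can be significant at reductions well short of 25%. A significant p-value would then sit beside a hypothesis that it does not address.

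The set of tests is also a poor fit for the question. The hypothesis is about a percentage reduction in dose, and Section 5.3 itself names the mean as the summary. Neither rank test estimates a percentage change in a mean. The signed-rank test needs paired observations, whereas the guided and control arms are independent groups.

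What is at stake is the wording of one secondary claim. It is a visible claim, because reducing ICS over-treatment is one of the trial's two stated aims and cumulative dose is the listed endpoint that measures it directly.

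**Working it through.** **The plan's own figure.** There is none to reproduce: the protocol gives no standard deviation, power or sample size for cumulative ICS dose.

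**Inputs**

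- 222 participants per side of the ICS comparison (Section 5: 444 as 222 x 2).
- Threshold: a reduction of 25%, that is, a guided/control ratio of 0.75 (Section 3).
- Assumed, because not in the protocol: a common standard deviation equal to CV times the control mean, with CV = 0.4, 0.6 or 0.8; two-sided 5% level; normal approximation.

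**Step 1. Test against no difference, as named in Section 5.3.** With the control mean set to 1, the standard error of the relative difference is SE = CV x sqrt(2/222) = CV x 0.0949. The smallest observed reduction that is significant is 1.96 x SE. The probability of a significant result in the direction of a reduction is Phi(true reduction/SE − 1.96).

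| CV | SE | Smallest significant observed reduction | P(significant), true 15% | P(significant), true 20% |
|---|---|---|---|---|
| 0.4 | 0.038 | 7.4% | 0.98 | >0.99 |
| 0.6 | 0.057 | 11.2% | 0.75 | 0.94 |
| 0.8 | 0.076 | 14.9% | 0.51 | 0.75 |

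For example, at CV 0.6 and a true 15% reduction: 0.15/0.0569 − 1.96 = 0.67, and Phi(0.67) = 0.75.

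At true reductions of 15% and 20% the hypothesis is false, yet the test is significant in at least half of trials across this range. Widening the range does not change the picture: the smallest significant reduction is 5.6% at CV 0.3 and 18.6% at CV 1.0, still below 25%.

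**Step 2. Test against the 25% threshold.** The null hypothesis is that the guided mean is at least 0.75 times the control mean. The standard error of (0.75 x control mean − guided mean) is SE2 = CV x sqrt((1 + 0.75²)/222) = CV x 0.0839. The observed reduction needed is 0.25 + 1.96 x SE2. Power is Phi((true reduction − 0.25)/SE2 − 1.96).

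| CV | SE2 | Observed reduction needed | Power, true 40% | Power, true 50% | Power, true 80% |
|---|---|---|---|---|---|
| 0.4 | 0.034 | 31.6% | 0.99 | >0.99 | about 1.00 |
| 0.6 | 0.050 | 34.9% | 0.85 | >0.99 | about 1.00 |
| 0.8 | 0.067 | 38.2% | 0.61 | 0.96 | about 1.00 |

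At a true reduction of exactly 25%, the chance of a positive finding is 2.5%, as it should be. At CV 1.0, power is 0.43 at a true 40% reduction and 0.85 at a true 50% reduction.

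**The case against.** The best defence is that Section 3 states a secondary hypothesis, not a decision rule. Nothing in the protocol says that p<0.05 would be taken as proof of a reduction above 25%. Section 5.3 gives no null value, and the mean doses it specifies would let a percentage reduction be reported next to the 25%. A null value, an estimator and a confidence limit are commonly left to an analysis plan, which is not at hand. The standard deviations and the true reductions of 15% and 20% used above are assumptions. If the real reduction is large, the stricter test changes nothing.

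Much of this stands, and it limits the weight of the point. It does not remove it: the protocol itself states both the threshold and the tests, the two do not meet, and an analysis plan that carried Section 5.3 over would inherit the gap. The signed-rank test is out of place whatever threshold is used.

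Three stronger readings are tempting, and the protocol does not support them.

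- **That the measurement period differs between Sections 5.2 and 5.3.** Sections 4.7 and 4.8 use the term study period for each participant's 12 months. Section 5.3 uses it for new-onset diabetes, which the list of exploratory endpoints defines over 365 days. Section 5.2 counts another endpoint's 365 days from recruitment. The two descriptions can therefore mean the same window. At most, the start point is loosely worded, since the primary endpoint in Section 5.1 counts from randomisation.
- **That 25% is a small fraction of what the trial expects.** Section 10 says only that a future treatment plan "has the potential to reduce the usage of ICS by 80" percent, based on the share of class C/D patients with high eosinophil counts. This is an aspiration in a perspective section, not a planning assumption for this trial.
- **That a modest reduction would mean failed separation and a biased non-inferiority result.** The intervention switches ICS on and off by repeated counts. Continued ICS at high counts is the strategy as designed, so a reduction short of 80% is not in itself failed delivery.

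**Conclusion.** The point holds as a mismatch between a stated threshold and the tests named for it. With 222 per side and an assumed standard deviation of 40% to 80% of the control mean, a true reduction of 15% gives a significant result with probability about 98% to 51%. These probabilities rest on that assumed spread, a common standard deviation and a normal approximation. The conclusion that significance can occur below 25% holds across CVs from 0.3 to 1.0. Two of the three named tests do not estimate the quantity in the hypothesis, and one of those is a paired test.

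Severity is minor. One secondary claim is affected. The primary analysis, the sample size and the data collection are not, and if the true reduction is near 80% the 25% bound is cleared almost with certainty.

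**What to change.** In Section 5.3 (Data analysis):

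1. Define the measure as cumulative budesonide-equivalent ICS dose over 365 days from randomisation, which also aligns the start point with Section 5.1.
2. Estimate the guided/control ratio of mean cumulative dose with a 95% confidence interval, and call the hypothesis of a reduction above 25% supported only if the upper limit is below 0.75.
3. Delete the Wilcoxon signed-rank test. If the Mann-Whitney test is kept, label it as supportive and not as evidence on the 25%.
4. Report the achieved reduction beside the non-inferiority result, so that readers can see how far ICS use differed between the strategies.

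The alternative is to keep a test against no difference and reword the hypothesis in Section 3 as any reduction in ICS use.

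Either route is a change of wording and needs no new data. It should be settled before unblinding. The price of the first route is a stricter criterion for one secondary claim: under the assumed spread, the observed reduction must reach about 32% to 38%.
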